7.3 Unblinding Procedures

Unblinding the study therapy is not commonly necessary but may be done if required to ensure a subject's safety. In most cases, the unblinding will be part of managing an SAE, and will be reported with the SAE. In cases where unblinding was not associated with an SAE, such actions will be reported in a timely manner (e.g., notification of IRB within 24 hours by phone or fax, followed by a written narrative of the event within 48 hours.). Otherwise, un-blinding will not be done until each phase of the study is complete (that is, when Phase 2 is finished running all enrolled participants, we can unblind the data).

7.4 Stopping Rules/Intervention Discontinuation

This study will be stopped prior to completion if: (1) the intervention is associated with adverse effects that call into question the safety of the intervention; (2) difficulty in study recruitment or retention will significantly impact the ability to evaluate the study endpoints; (3) any new information becomes available during the trial that necessitates stopping the trial; or (4) other situations occur that might warrant stopping the trial.

8.0 STATISTICAL CONSIDERATIONS

8.1 Summaries of Design, Endpoints, and Analysis

8.1.1 Phase II: Study Design/Study Endpoints

Enroll and randomize 220 CBP patients into the study. Stratify into placebo responders and non-responders based on brain scan results at entry. We anticipate that about 50% of the patients will be placebo responders. All participants are randomized so that 40 receive placebo treatment, 40 active medication, and 20 no treatment. If Gender Supplement is awarded then randomization is slightly different: 60 receive placebo, 60 active medication, and 20 no treatment.

We assume that placebo responders and non-responders will show differential interaction with active medication treatment. We also expect to distinguish the four groups based on brain activity at the end of the trial, and show close correspondence between predicted and actual outcomes regarding placebo responses. Additionally, placebo non-responders should show a robust medication response, especially in comparison to the placebo non-responders receiving placebo treatment. Brain activity contrasts are done as a two-way (treatment groups) repeated measures (time: start vs. end) ANOVA (2RM-ANOVA). This is the procedure we implemented recently in a longitudinal neuroimaging study of pain chronification (Baliki et al., 2012). Post-hoc comparisons then reveal: 1) A contrast of brain activity at end of treatment between placebo non-responders with and without medication treatment to identify brain activity for bottom-up modulation of chronic pain. 2) Brain regions related to chronic pain are identified as areas commonly decreased with placebo treatment for placebo responders and medication treatment for placebo non-responders. 3) Top-down placebo and bottom-up medication effects are distinguished by identifying regions that distinctly increase in activity for placebo and medication treatments based on contrasts for the same groups. 4) The no treatment group brain activity is used as a higher-level contrast, which effectively corrects for this confound.

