11. PUBLICATIONS -----27

12. REFERENCES -----28

13. SUPPLEMENTS/APPENDICES ----- 32

 I CONSENT FORM TEMPLATE ----- 32

 II LIST OF QUESTIONNAIRES ----- 40

 III AE COLLECTION FORM TEMPLATE ----- 41

 IV DSMP ----- 42

 V STUDY ROSTER -----111

 VI SCHEDULE OF EVALS & ASSESSMENTS ----- 114

 VII BIostatistician CV ----- 117

 VIII LABORATORY PROCEDURES & EVALUATIONS ----- 126

STUDY SCHEMA AND DESIGN

Design Schema for Objective 2 (Phase 2):

We intend to randomize 210 CBP patients into the study with the expectation that 140 will finish successfully. The entire duration of the study will be 12 weeks with an initial 3-week baseline period (visits 1-3), a 6-week treatment period (visits 3-5), and a final 3-week washout period (visits 5-6). During the baseline period eligible **participants will be predicted as placebo responders and non-responders** based upon baseline brain scan results and specific questionnaire answers (properties determined from the results of **Phase 1**) and then classified on that basis. Participants will then be randomized within each classification group (placebo responders and placebo non-responders) at a ratio of 3:3:1 such that 42.5% receive active medication (naproxen/omeprazole, 500/20mg, bid), 42.5% receive matching placebo treatment and 15% no treatment. Brain imaging, self-report questionnaire, and pain/mood rating measurement regimens are shown in **Figure 1**. Pain, mood, and pill ingestion will all be monitored by smart phone for the duration of the study, as well as determined in person at each visit.

[figure not shown]

Figure 1. Experimental schema for Phase 2. Expected changes in pain are shown in solid and dashed horizontal lines. We expect to see different pain outcomes for the various placebo and treatment combination groups. To be noted, we predict that the No Treatment group will have similar pain trajectory as those classified Non-responders and treated with placebo. As well, in the No Treatment group participants will be classified as placebo responders and placebo non-responders, but will not receive any treatment agent, therefore, their pain trajectory will be constant throughout the study.

STUDY SUMMARY

Title	BRAIN MECHANISMS FOR CLINICAL PLACEBO IN CHRONIC PAIN
Short Title	PLACEBO IN CHRONIC PAIN (PICP)
Protocol Number	Grant:
Phase	Grant Phase 2
Methodology	Double blind, randomized (see section 5.4 for more specifics on blinding)
Study Duration	12 weeks
Study Center(s)	Northwestern University

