whether or not they took their medication. This will allow us to keep track of the stability and magnitude of pain and mood, as well as treatment compliance. To encourage them to keep up with this requirement, each time they submit these answers, they will receive 25 cents. Responses and payments will be logged automatically into a secure database that only study personnel will have access to; if participants miss more than 3 consecutive ratings in a row, research personnel will call or text them to remind them to rate or verify that their app is still working (they are automatically alerted via email by a program designed by the lab). The unblinded monitor designated for this study will check participants ratings bi-weekly to verify that ratings are being completed.

- Follow up: Patients will be asked if they wish to be added to our contact list to participate in future studies of the lab. They will also be asked if they accept to be contacted by phone 3 months and 6 months later to assess the long-term effects of the study intervention on their chronic pain intensity.

5.3 Randomization:

All randomization (and blinding, see next section) will be completed by NUCATS (see study roster in Location 2 for name of personnel). NUCATS will generate two randomization sequences, one for each group (predicted responders, Group A, and non-responders, Group B). This approach will ensure the proper 3:3:1 treatment allocation. We will use a variable block design (size of 5 and size of 10), throughout Phase 2 of the study to minimize temporal bias that can accompany longitudinal scanning studies. We don't anticipate much exclusion after randomization and enrollment based on our previous studies (although screen failures during the run-in are likely due to pain level or pathology lab results, for example). The Phase 2 overall sample size is 210 randomized 3:3:1, therefore n = 90 active treatment (n = 45 responders/non-responders), n = 90 placebo treatment (n = 45 responders/non-responders), and n = 30 no treatment (n = 15 responders/non-responders). We expect an attrition rate of ~33% for a final N = 140.

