8.1.2 Sample Size and Accrual

Statistical power can be estimated based on the Cohen's d effect sizes for differences in pain with 6 weeks of treatment. For responders, based on our preliminary results, we anticipate a mean decrease of 2.5 units on a 0-10 scales with an estimated SD of 3, which results in an effect size estimate of 0.83. In non-responders, the mean decrease in pain is negligible and we do not expect to have enough power to detect this.

Power analyses in G*Power 3.1.3 indicated that we will have ample power to detect pre-to-post changes within a group; with an estimated effect size of $d = 0.8$, power would exceed 95% with a sample of 23 participants. In terms of a between-group comparison, assuming an effect size estimate of $d = 0.8$ across groups, power would exceed 95% for a sample size of $n = 42$ per group. Thus, the total sample size of 210 would provide for adequate power, even accounting for

potential dropout and/or lower-than-expected effect sizes. Assuming that we recruited 70 participants per group, for example, would mean that we could detect between-group effects as small as $d = 0.5$ with power exceeding 80%.

Power analysis for gender: The preliminary gender analyses from phase 1 subjects provide the means to calculate the power necessary for detecting gender effects in placebo propensity. The original sample sizes from phase 1 were based on treating gender and age as covariates of no interest. Based on an anticipated medium-sized effect using Cohen's conventions (Cohen, 1992), calculations in `chi2power` in Stata indicated that for $n=82$ and for $\alpha = 0.05$ we obtain power = 0.31. Instead if we double the number of subjects then we reach adequate detection power: assuming that males have 30% while females 50% placebo incidence rate, for $\alpha = 0.05$ and $n=160$ we obtain just adequate power = 0.74. Therefore all data from phase 1 and 2 will be combined to assess effect of gender on placebo response.

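### Section 8.1.1 randomises 220 with arm counts that sum to 100 or 140, against 210 at 3:3:1 elsewhere; separately, the block sizes in 5.3 cannot hold 3:3:1

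*Combined protocol and SAP*

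**What the plan says.** Section 8.1.1 of the protocol gives a total, "Enroll and randomize 220 CBP patients into the study", and then two alternative splits. The base one is "All participants are randomized so that 40 receive placebo treatment, 40 active medication, and 20 no treatment". The other is conditional: "If Gender Supplement is awarded then randomization is slightly different: 60 receive placebo, 60 active medication, and 20 no treatment".

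The rest of the document gives a different total and one ratio:

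- Study Schema and Design: "We intend to randomize 210 CBP patients into the study with the expectation that 140 will finish successfully", allocated "at a ratio of 3:3:1 such that 42.5% receive active medication".
- Study Summary: 210 enrolled and 140 completing in Phase 2, with 340 across both phases (130 in Phase 1).
- Section 5.2.1, in the interim between Visits 2 and 3: 3:3:1 within each predicted-response class.
- Section 5.3: "The Phase 2 overall sample size is 210 randomized 3:3:1, therefore n = 90 active treatment", with 90 placebo and 30 no treatment, attrition of about 33%, and 140 at the end.
- Section 8.1.2: "the total sample size of 210 would provide for adequate power". It does not mention 3:3:1, and its worked example is 70 per group.

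On how the list is built, 5.3 says: "We will use a variable block design (size of 5 and size of 10". The same paragraph says that the approach will secure the 3:3:1 allocation.

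**The concern.** The number randomised and the allocation ratio are basic design figures, and the statistical section is where an analyst, auditor or monitor looks for them. Section 8.1.1 gives a total found nowhere else, and neither of its splits adds up to that total. The base split also has a ratio found nowhere else. The ratio that matches the other sections depends on an award whose outcome the document does not report.

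The block sizes are a separate defect. Correcting 8.1.1 would leave them in place, and they matter more in practice because they instruct the unit that generates the list. Someone building blocks of 5 and 10 has to depart from either the block sizes or the ratio.

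**Working it through.** **Inputs.** 8.1.1: 220; 40/40/20; 60/60/20. Schema and summary: 210 randomised, 140 completers, 340 = 130 + 210. Section 5.3: 90/90/30, attrition about 33%, blocks of 5 and 10. Section 8.1.2: total 210, example of 70 per group.

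**1. Reproduce 210.** Number to randomise = completers / (1 − attrition).
- 140 / (1 − 1/3) = 210. With 0.33 exactly, 140 / 0.67 = 209 after rounding up.
- Split 3:3:1: 210 × 3/7 = 90, 90, and 210 × 1/7 = 30. By class, 2 × (45 + 45 + 15) = 210.
- Two phases: 130 + 210 = 340.

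So 210, 90/90/30, 140 and 340 agree with one another.

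**2. Try to reproduce 220.**
- Sums in 8.1.1: 40 + 40 + 20 = 100 and 60 + 60 + 20 = 140.
- If those counts were completers at 33% attrition, 100 / 0.67 gives 150 and 140 / 0.67 gives 209.
- Attrition needed to go from 220 to 140: 1 − 140/220 = 36.4%. From 220 to 100: 1 − 100/220 = 54.5%. The plan states about 33%.
- 220 × 3/7 = 94.3, not a whole number.
- Two phases: 130 + 220 = 350, not 340.

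No stated input leads to 220. It exceeds 210 by 10 patients (10/210 = 4.8%).

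**3. Compare the ratios.**
- 40:40:20 = 2:2:1, no-treatment share 20/100 = 20%.
- 60:60:20 = 3:3:1, no-treatment share 20/140 = 14.3%.
- 90/90/30 × 2/3 = 60/60/20, so the conditional counts equal the completers expected under 5.3.

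Only the base split has the wrong ratio.

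**4. Check the block sizes.** A block that holds 3:3:1 exactly has a size that is a multiple of 3 + 3 + 1 = 7.
- Size 5: 15/7 = 2.14 per treatment arm and 5/7 = 0.71 no treatment. Size 10: 4.29 and 1.43. Neither is possible.
- Size 5 as 2 + 2 + 1 and size 10 as 4 + 4 + 2 hold 2:2:1 exactly.
- If blocks of 2:2:1 were used throughout, 210 patients would split 84/84/42 (210 × 2/5 and 210 × 1/5) instead of 90/90/30.

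**5. Check the power text.** Noncentral t, two-sided 0.05. The plan gives no alpha for the pain comparisons, so this level is assumed.
- 23 paired, d = 0.8: 95.6%. 42 per group, d = 0.8: 95.2%. 70 per group, d = 0.5: 83.6%. All three agree with 8.1.2.
- None of them uses 220 or 40/40/20.
- 3 × 70 = 210, so the example is an equal three-way split. For a replacement at d = 0.5: 90 v 90 gives 91.6% and 90 v 30 gives 65.3% on randomised numbers; 60 v 60 gives 77.5% and 60 v 20 gives 48.1% on completers.

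**The case against.** The strongest reply is that this is leftover text with little practical reach. The schema, 5.2.1 and 5.3 all give 3:3:1. Section 5.3 gives the explicit 90/90/30 and assigns the list to an independent unit, and nothing tells anyone to allocate from 8.1.1. The conditional split is exactly 3:3:1, and the gender objective (2.1.3) and the 140 completers suggest that it is the branch in force. Most of this stands for 8.1.1 and makes it a consistency error. It does not remove the 220, and it does not answer the block-size point, which sits in 5.3 itself. One could vary the make-up of blocks of 5 so that 3:3:1 holds over 35 patients (7 × 5), but 5.3 describes nothing of the kind.

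A reader might infer four stronger things that the documents do not support:

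- **That the trial loses power.** One could set 20 per class-by-arm cell (40/2) against 30 (60/2) and compute the loss for a drug-by-class interaction. But 8.1.1 presents the 40s as randomised, while 30 per cell is a completer count; the randomised count in 5.3 is 45. The plan also gives no effect size for that interaction: d = 0.8 in 8.1.2 is for pre-to-post change and for a comparison of two groups.
- **That 8.1.2 supports 3:3:1.** It supports 210 only.
- **That 60/60/20 is stated to be completers.** Section 8.1.1 presents it as randomisation. The completer reading is an inference from 90/90/30 × 2/3.
- **That the block sizes survive from a 2:2:1 plan, or that patients will be allocated 2:2:1.** The fit is suggestive, but the document says neither.

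**Conclusion.** The point holds as an inconsistency in the current text, in three parts. First, the 220 in 8.1.1 contradicts 210 in four other places, cannot be derived from any stated input, and matches neither arm split given beside it. Second, the base split of 40/40/20 contradicts 3:3:1; the conditional 60/60/20 does not, but the document leaves its condition open. Third, blocks of 5 and 10 in 5.3 cannot deliver the 3:3:1 that the same paragraph promises.

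The size is 10 patients in the total and, only if blocks really held 2:2:1, 20% rather than 14.3% in the no-treatment arm (42 rather than 30 of 210). The stated power figures reproduce and are unaffected by 8.1.1. The mismatch in 8.1.2 is limited to an example that assumes equal groups. Taking 210 as the intended figure rests on its agreement across the schema, summary, 5.3 and 8.1.2, and on the attrition arithmetic.

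**What to change.** - **8.1.1:** state 210 randomised at 3:3:1 (90 placebo, 90 active, 30 no treatment), with about 60/60/20 expected to complete after one-third attrition. Remove 220 and 40/40/20.
- **Supplement:** the sponsor should confirm whether it was awarded. If so, remove the condition and align the related text at the end of 8.1.2 (a 50% increase in the treatment groups) and in the sample size justification of the Data and Safety Monitoring Plan (an additional 40 patients). If not, the 210 at 3:3:1 elsewhere must itself be reconciled with 8.1.1.
- **8.1.2:** replace the 70-per-group example with the 3:3:1 group sizes, saying whether they are randomised or completing, and give power for the treatment comparison and the no-treatment comparison separately.
- **5.3:** for any list not yet generated, use block sizes that are multiples of 7, for example 7 and 14. If the list already exists, report the ratio and block sizes actually used.

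The cost is text edits in these sections and, at most, generating a list not yet made. No extra patients are needed.

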- Visit 2 (week -1): Baseline Scan (90 min). Approximately 14 days after visit 1, participants will return for their second visit. If a VAS score of > 5 mm on average over the course of the visit 1-visit 2 rating period is calculated and no changes in clinical status are reported or found, they complete a battery of questionnaires and undergo MRI procedures (anatomical and functional scans). Subjects will be queried about changes to health experienced since the last visit and asked if they exceeded 4 acetaminophen per day. In addition one of the pictures for visit 2, 4, and 5 will be conducted (see section 13.III). They will be asked to continue their phone/computer app ratings and return in approximately one week for visit 3. Participants will receive only rescue medication in sufficient quantities until the next visit. Additionally, participants will be randomized into a treatment versus no-treatment group at this time (information that the pharmacy will produce and keep).
- Interim between Visit 2 and Visit 3: Group classification Based on Predicted Response

In between visits 2 and 3, participant's scans will be analyzed by extracting the functional connectivity between frontal and sensorimotor networks (called "sign permutation" in Equation 1) and 2 questionnaire subscores will be calculated (MAIA emotion and ERQ suppression in Equation 1); all 3 parameters will then be entered into Equation 1. Based on the results of the model specified on page 10, participants will be classified as either placebo non-responders (probability < 0.5) or placebo responders (probability \geq 0.5).

After baseline scan, the subjects' MR images and data will be collected by research personnel and then will be given to a single member, the blinded assessor ([name]) who will have no interaction with the participants, therefore will remain blinded. The research personnel responsible for conducting the visit will download the MAIA and ERQ questionnaires from the REDCap database and calculate the scores for MAIA-Emotion and ERQ-suppression subscales to be used in the model.

(1) All MR images collected at the baseline scan will be uploaded to the server and pre-processed within 24 hours of the visit using our in-house pipeline.

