- Visit 5 (week 6): End of Treatment/Start of Washout and Final Scan (60-90 min): Participants will undergo the same brain scanning session that they had on Visit 2, and all questionnaires, AE assessment, and treatment medication adherence procedures will be performed as they were in previous visits. Participants will be asked to stop the study medication (if applicable) and to start the washout period, and they will only be given rescue medication at this visit by the research staff (enough to last them until the last visit). In addition one of the pictures for visit 2, 4, and 5 will be conducted (see section 13.III). They will be asked to continue rating their pain and mood on the app and to return for the final visit in 3 weeks. Note that apart from the scanning session and administration of questionnaires via REDCap, all other aspects of this visit will be completed by the unblinded monitor to aid in the maintenance of the double-blind on the part of the study staff.
- Visit 6 (week 9): Final Visit/End of Washout (30-45 min): Any changes to health will be documented, and vitals will be collected. A short battery of questionnaires will be administered and participants will be compensated for all app ratings completed during the study.
- Interim periods: During weeks in between visits, participant data will be tracked with the assistance of a smart phone/computer application designed for the study (available through a secure website). Depending upon preference, we will download an app onto participants' phones or give them a link to use on their computers; in the case that a participant does not have a smart phone or easy access to a computer/internet, we will provide him/her with a smart phone that has the app already installed. Participants will be given a login and will be asked to use this application twice a day, morning and night for baseline and washout and right after they take their medication for treatment (if applicable). The app asks them to rate the severity of their pain and their mood on a Likert scale, and probes them as to

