Our previous fMRI results show that 20 per group should be adequate given the preliminary results and earlier studies. Also, 20 per group allows for 80+% statistical power for effect sizes of 1 SD difference between groups. For DTI and T1 studies our earlier studies indicate that 20/group for within-subject contrasts is adequate but may be just at the limit for whole-brain contrasts for detecting between-group differences. We can overcome this obstacle by using targeted analyses of relevant brain areas. For example, simply removing the cerebellum and occipital cortex voxels from such analyses results in improving on multiple comparison cost by a factor of 2.

The results from Phase 1 affirm the above power calculations. Moreover they indicate that increasing the n for each of the treatment groups by 50% (as proposed in the gender supplement application) can lead to identifying effects that currently remain either non-significant or borderline significant.

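### Post-hoc brain contrast 1 is worded as an end-of-treatment comparison with no adjustment for the Visit 2 scan, which gives up precision that the collected data could supply

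*Combined protocol and SAP*

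**What the plan says.** Section 8.1.1 sets the parent analysis: "Brain activity contrasts are done as a two-way (treatment groups) repeated measures (time: start vs. end) ANOVA (2RM-ANOVA"). The Study Summary repeats this. Both scans are therefore in the parent model.

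Four numbered items then follow under the words "Post-hoc comparisons then reveal". The first, meant to show how medication modulates chronic pain from the bottom up, is "A contrast of brain activity at end of treatment between placebo non-responders with and without medication treatment". No change score and no baseline covariate is attached to it. Items 2 and 3 are worded differently: they look for regions that fall or rise in activity, which implies change over time. Item 4 brings in the no-treatment group as a higher-level contrast. No section names baseline adjustment for any imaging contrast.

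The baseline measurement exists. At Visit 2 participants who still qualify on pain are scanned ("they complete a battery of questionnaires and undergo MRI procedures (anatomical and functional scans"), and at Visit 5 "Participants will undergo the same brain scanning session that they had on Visit 2" (section 5.2.1).

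For imaging power, section 8.1.2 says that "20 per group allows for 80+% statistical power for effect sizes of 1 SD difference between groups".

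**The concern.** Brain measures differ between people for reasons unrelated to six weeks of treatment. A comparison of week-6 values alone leaves all of that variation in the error term. Where the same measure was taken before treatment, part of it can be removed at no cost in data.

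The wording also leaves three readings of contrast 1 open: a simple effect at the end of treatment, a difference in change (the group-by-time term), or a baseline-adjusted difference. They have different standard errors and, voxel by voxel, can give different maps. An analyst could choose among them after seeing the results.

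Precision is scarce here. The cells are small, and section 8.1.2 itself describes whole-brain between-group contrasts for DTI and T1 as possibly at the limit of what the sample supports.

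**Working it through.** **Inputs**

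- Cell size. Section 5.3 gives "n = 90 active treatment (n = 45 responders/non-responders), n = 90 placebo treatment (n = 45 responders/non-responders"), read as 45 in each predicted class, with about 33% attrition to 140 completers. If attrition is even, each active or placebo cell has 140 × 3/7 ÷ 2 = 30 completers. Section 8.1.1 gives 40 or 60 per treatment arm, which is 20 or 30 per cell if half are predicted responders. The main figures use 30.
- Alpha. No imaging alpha is stated. The gender calculation uses 0.05 ("for $\alpha = 0.05$ and $n=160$ we obtain just adequate power = 0.74"). Two-sided 0.05, uncorrected for multiple voxels, is assumed here.
- Comparison. Section 8.1.1 does not say whether those without medication include the no-treatment arm. Its preceding sentence compares with non-responders on placebo, so active versus placebo is assumed.
- Scan-rescan correlation rho. Not in the documents. The range 0.3 to 0.7 is an assumption.

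**The plan's own figure.** A two-sample t-test with 20 per group and a 1 SD difference has power 86.9% (88.5% by normal approximation). This agrees with the stated 80+%.

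**Formulas.** Error variance relative to an end-only comparison, with equal variances at the two visits:

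- end-only: 1
- change score (the group-by-time term with two time points): 2(1 − rho)
- baseline-adjusted (ANCOVA): 1 − rho²

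The detectable difference is the end-only value times the square root of the relative variance. The equivalent end-only sample is n divided by the relative variance. The one degree of freedom spent on the covariate is ignored.

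**Results, 30 per cell.** The end-only comparison detects d = 0.736 at 80% power and has 76.0% power at d = 0.7. Here d is in units of the end-of-treatment SD.

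| rho (assumed) | Method | Relative variance | Detectable d | Power at d = 0.7 | Equivalent end-only n per cell |
|---|---|---|---|---|---|
| 0.3 | ANCOVA | 0.91 | 0.70 | 79.8% | 33 |
| 0.3 | Change | 1.40 | 0.87 | 61.5% | 21 |
| 0.5 | ANCOVA | 0.75 | 0.64 | 86.8% | 40 |
| 0.5 | Change | 1.00 | 0.74 | 76.0% | 30 |
| 0.7 | ANCOVA | 0.51 | 0.53 | 96.2% | 59 |
| 0.7 | Change | 0.60 | 0.57 | 93.1% | 50 |

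For example, at rho = 0.5, 0.736 × √0.75 = 0.64 and 30 ÷ 0.75 = 40.

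At 20 per cell the end-only detectable d is 0.91. ANCOVA lowers it to 0.87 at rho = 0.3 and 0.65 at rho = 0.7.

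**ANCOVA against change.** The variance ratio is 2(1 − rho) ÷ (1 − rho²) = 2 ÷ (1 + rho), which is never below 1. So ANCOVA is at least as precise as a change score at any rho. A change score is less precise than the end-only comparison when rho is below 0.5.

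**The case against.** The strongest reply is that the parent model already contains the baseline scan. A reader might infer from contrast 1 that the plan ignores the Visit 2 scan. Section 8.1.1 does not support that: the model is start versus end, and items 2 and 3 are about change. What stands is narrower. A group comparison fixed at the end of treatment does not gain from the baseline scan merely because the parent model includes it. If contrast 1 is instead meant as the group-by-time term, it is a change score, which ANCOVA still equals or betters.

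A reader might also infer that chance baseline imbalance could bias the drug comparison. It does not. Allocation is randomised within each predicted class (sections 5.2.1 and 5.3), so the end-only comparison is unbiased and chance imbalance is already part of its nominal error rate.

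Nor do the documents make contrast 1 the decisive drug analysis. The four items are not ranked, medication also enters items 2 and 3, and the endpoint in section 2.3.1 for the primary objective is pain response.

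The size is open to challenge as well. It rests on an assumed rho, and at 0.3 the gain is small (76.0% to 79.8% power at d = 0.7). The uncorrected alpha means that the power figures are not those of a whole-brain analysis. The variance ratios do not depend on alpha and do carry over.

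Finally, it is tempting to ask for baseline adjustment in every post-hoc contrast. That would be wrong for items 2 and 3. They involve placebo in predicted responders and medication in predicted non-responders. Those cells are not randomised against each other, and their strata are defined partly by baseline frontal-sensorimotor connectivity (Equation 1, section 2.1.4). Adjusting across groups that differ at baseline by construction targets a different quantity from change and can produce an apparent difference.

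**Conclusion.** The point holds as one of precision and clarity for contrast 1 alone. As worded, it is an end-of-treatment comparison with no stated adjustment for a scan that the trial collects. Within predicted non-responders, active versus placebo is a randomised comparison, so ANCOVA on the Visit 2 measure is valid and, apart from one degree of freedom, at least as precise as either other reading.

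The gain over end-only runs from modest to large: detectable d falls from 0.74 to between 0.70 and 0.53, or about 1.1 (1 ÷ 0.91) to 2.0 (1 ÷ 0.51) times the sample. This assumes rho between 0.3 and 0.7, 30 completers per cell with even attrition, and two-sided alpha 0.05 without whole-brain correction. The documents cannot say where in that range the trial lies. They do not support the stronger readings that the plan discards the baseline scan or that contrast 1 is biased.

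**What to change.** In section 8.1.1, state contrast 1 as follows: within predicted placebo non-responders, the Visit 5 measure is regressed on arm (active versus placebo), adjusted for the same measure at Visit 2. For regional or voxel-wise analyses the covariate is the Visit 2 value of that region or voxel. Say that the comparator is the placebo arm, if that is the intention.

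Limit this to measures acquired at both visits. Section 5.2.1 describes the Visit 5 session as the same as Visit 2, but the schedule of evaluations in the appendix lists T1, resting and DTI scans at Visit 2 and adds pain rating scans at Visit 5. Reconcile the two. If the pain rating scan is done only at Visit 5, it has no baseline and cannot be adjusted in this way.

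Leave contrasts 2 and 3 as change-based comparisons.

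The cost is a change of analysis wording, made before unblinding. No new data are needed for measures scanned at both visits.
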